## 9.4 Post-Treatment Phase

### 9.4.1 Treatment Discontinuation

**The revised Schedule of Assessments shown in [Table 3](#) replaces all prior schedules of assessments as of implementation of Protocol Amendment 5.**

Upon treatment discontinuation, regardless of the reason, patients will have a Treatment Discontinuation visit. The following procedures will be performed:

- Tumor scans (using the same methodology as was used at screening) if reason for treatment discontinuation was other than disease progression based on radiologic assessment
- CA-125 measurement
- Study drug accountability

The following procedures are advised:

- ECOG performance status ([Appendix D](#))

- Hematology (complete blood count)
- Clinical chemistry, urinalysis, and vital signs according to local standard of care per investigator
- Serum chemistry (fasting is not required)
- Serum pregnancy test for women of child-bearing potential
- AE monitoring
- Optional tumor tissue biopsy collection at time of disease progression/treatment discontinuation until the start of the subsequent anticancer treatment (requires additional consent). If disease progression is caused by appearance of a new lesion(s), the lesion(s) should be prioritized for the optional biopsy. Tumor tissue will be processed locally as FFPE tissue. Refer to the Pathology Charter for detailed sample handling instructions.

#### **9.4.2 28-day Follow-up**

The following procedures will be performed for all patients at 28 ( $\pm 3$ ) days after the last dose of study drug:

- Disease assessment for patients who discontinued treatment for reason other than disease progression or death. Tumor scans should continue to be performed at 12-week intervals (up to 7 days prior permitted) until radiologic disease progression by RECIST v1.1, as assessed by the investigator. Patients who have been on study at least 18 months may decrease the frequency of disease assessments to every 16 ( $\pm 2$ ) weeks. Investigator should consult with sponsor's medical monitor before decreasing frequency.
- AE monitoring (only SAEs/AESIs are recorded through 28 days after last dose of rucaparib. Ongoing SAEs and AESIs will be followed until resolution, stabilization, or lost to follow-up).
- Subsequent treatments, secondary malignancy monitoring, and overall survival (OS)

#### **9.4.3 Long-term Follow-up**

- Disease assessment for patients who discontinued treatment for reason other than disease progression or death. Tumor scans should continue to be performed at 12-week intervals (up to 7 days prior permitted) until radiologic disease progression by RECIST v1.1, as assessed by the investigator. Patients who have been on study at least 18 months may decrease the frequency of disease assessments to every 16 ( $\pm 2$ ) weeks. Investigator should consult with sponsor's medical monitor before decreasing frequency.
- Subsequent treatments, secondary malignancy monitoring, and OS information will be collected for all patients approximately every 12 weeks ( $\pm 14$  days) until death, loss to follow-up, withdrawal of consent from study, or closure of the study. Follow-up can be performed via the telephone. Diagnosis of any secondary malignancy requires appropriate documentation (i.e., laboratory and/or pathology reports) and should be reported as indicated in [Section 10.8](#).

- SAEs related to study drug and all AESIs, irrespective of causality, are to be reported as specified in [Section 10.8](#).

## **9.5 Methods of Data Collection**

Hematology, clinical chemistry, urinalysis, serum CA-125, and serum pregnancy in women of child-bearing potential will be performed locally.

### **9.5.1 Pharmacokinetic Evaluations and AAG Measurement**

**As of implementation of Protocol Amendment 5, samples will no longer be collected for PK and AAG analyses.**

### **9.5.2 Biomarker Analysis – FFPE Tumor Tissue**

Archival tumor tissue must be located during the screening process and submitted **to the central laboratory directly** as soon as possible for determination of HRD status. Archival tumor tissue is required for HRD stratification for randomization and for storage for potential bridging to a validated companion diagnostic test.

### **9.5.3 Biomarker Analysis – Blood**

As of implementation of Protocol Amendment 5, blood samples will no longer be collected for biomarker analyses.

### **9.5.4 Safety Evaluations**

#### **9.5.4.1 Adverse Event Assessment**

The investigator is responsible for assessing the safety of the patients and for compliance with the protocol to ensure study integrity. Patients will be monitored for AEs during study participation, beginning after the first dose of study drug and until 28 days after the last dose of study drug. Any ongoing SAEs and AESIs will be recorded and followed until resolution, stabilization, or loss to follow-up. Only treatment-related SAEs and all AESIs, regardless of causality, need to be reported after the 28-day window. SAEs will be graded according to the NCI-CTCAE grading system (v4.03) and recorded on the eCRF.

Complete details for monitoring AEs, including the definition of drug-related AEs, are provided in [Section 10](#).

#### **9.5.4.2 Prior and concomitant medications**

Prior concomitant medications will be recorded during screening and concomitant medications will be collected from study entry until the Treatment Discontinuation visit.

### 9.5.4.3 Clinical Laboratory Investigations

Certified local laboratories will perform study-related clinical laboratory tests according to institutional procedures, and the results will be reviewed by the investigator. The panels of laboratory tests to be performed are shown below:

**Hematology:** As of implementation of Protocol Amendment 5, monthly hematology assessment, consisting of a complete blood count, is advised.

**Clinical Chemistry:** As of implementation of Protocol Amendment 5, clinical chemistry assessments may be performed according to local standard of care per investigator.

**Urinalysis:** As of implementation of Protocol Amendment 5, urinalysis may be performed according to local standard of care per investigator.

Laboratory reports should be reviewed by the investigator or delegated physician who will assess clinical significance.

**Serum Pregnancy:** For women of child-bearing potential only. Serum pregnancy testing is to be performed  $\leq 3$  days prior to first dose of study drug,  $\leq 3$  days prior to the start of every cycle during the treatment phase, and at the Treatment Discontinuation visit.

### 9.5.4.4 Vital Signs

As of implementation of Protocol Amendment 5, vital signs may be performed according to local standard of care per investigator.

### 9.5.4.5 12-Lead Electrocardiograms

As of implementation of Protocol Amendment 5, ECGs will no longer be a required procedure for this protocol.

### 9.5.4.6 Body Weight and Height

As of implementation of Protocol Amendment 5, body height and weight assessments will no longer be a required procedure for this protocol.

### 9.5.4.7 Physical Examinations

As of implementation of Protocol Amendment 5, physical examinations will no longer be a required procedure for this protocol.

### 9.5.4.8 ECOG Performance Status

As of implementation of Protocol Amendment 5, ECOG performance status assessments will no longer be a required procedure for this protocol.

## **9.5.5 Efficacy Evaluations**

### **9.5.5.1 Disease Assessments**

Tumor assessment measurements will be performed at screening, at the end of every 12 weeks of treatment (up to 1 week prior permitted) relative to Cycle 1 Day 1, at discontinuation of treatment, and as clinically indicated. Patients who have been on study at least 18 months may decrease the frequency of disease assessments to every 16 ( $\pm 2$ ) weeks. Investigator should consult with sponsor's medical monitor before decreasing frequency.

Disease assessment will comprise clinical examination and appropriate imaging techniques (CT scans of the chest, abdomen, and pelvis with appropriate slice thickness per RECIST); other studies (MRI, X-ray, PET, and ultrasound) may be performed if required. If a patient has known brain metastases, this disease should be evaluated at each required assessment. The same methods used to detect lesions at baseline are to be used to follow the same lesions throughout the clinical study. CT/MRI scans of the chest, abdomen, and pelvis performed to determine the extent of disease at baseline should also be performed at each time of disease assessment, even if the scans were negative at baseline. Investigators should perform scans of other anatomical sites that, in their judgment, are appropriate to assess based on each patient's tumor status. Imaging guidelines provided in the Bioclinica Site Manual should be followed for the collection of images and the radiological assessment of disease.

Tumor response will be interpreted using RECIST v1.1 ([Appendix B](#)). Disease progression will only be determined by RECIST v1.1. Patients with a CR at study entry will only be considered to have disease progression if a new lesion is identified. Patients who meet GCIG CA-125 criteria for disease progression should have a radiologic assessment and be assessed by RECIST. If the radiologic assessment does not confirm disease progression, patients should continue on treatment and continue to be assessed by RECIST v1.1 per the protocol schedule of assessments.

Patients who discontinued treatment for reason other than disease progression or death should continue to have tumor scans performed at 12-week intervals (up to 7 days prior permitted) until radiologic disease progression by RECIST v1.1, as assessed by the investigator. Patients who have been on study at least 18 months may decrease the frequency of disease assessments to every 16 ( $\pm 2$ ) weeks. Investigator should consult with sponsor's medical monitor before decreasing frequency.

### **9.5.5.2 Tumor Markers**

CA-125 measurement will be performed at screening, on Day 1 of Cycle 1, at the start of every 3rd cycle thereafter (i.e., Day 1 of Cycle 4, Cycle 7, Cycle 10, etc.), at discontinuation of treatment, and as clinically indicated.

## **9.5.6 Patient-Reported Outcomes**

With the implementation of Protocol Amendment 4, the collection of patient-reported outcomes was no longer required.

### ***9.5.7 Appropriateness of Measurements***

The assessments planned in the protocol are widely used and recognized as reliable, accurate and relevant.

## **10 ADVERSE EVENT MANAGEMENT**

### **10.1 Definition of an Adverse Event**

An AE is any untoward medical occurrence, including the exacerbation of a pre-existing condition, in a patient administered a pharmaceutical product. The pharmaceutical product does not necessarily have a causal relationship with the AE. Anticipated fluctuations of pre-existing conditions, including the disease under study, that do not represent a clinically significant exacerbation or worsening are not considered AEs.

For the purposes of this study, disease progression of the patient's tumor with new or worsening symptoms must be documented as an AE. However, disease progression documented solely by radiographic evidence with no new or worsening symptoms will not require reporting as an AE.

It is the responsibility of the investigator to document all AEs that occur during the study. AEs should be elicited by asking the patient a nonleading question (eg, "Have you experienced any new or changed symptoms since we last asked/since your last visit?"). The existence of an AE may be concluded from a spontaneous report of the patient; from the physical examination; or from special tests such as the ECG, laboratory assessments, or other study-specified procedure (source of AE). AEs will be reported on the AE eCRF. Symptoms reported spontaneously by the patient during the physical examination will also be documented on the AE eCRF.

### **10.2 Definition of a Serious Adverse Event**

An SAE is any untoward medical occurrence that occurs at any dose that:

- Results in death.
- Is immediately life-threatening (i.e. the patient is at risk of death at the time of the event; it does not refer to an event that hypothetically might have caused death if it were more severe).
- Requires in-patient hospitalization or prolongation of existing hospitalization.
- Results in a persistent or significant incapacity or substantial disruption of the ability to conduct normal life functions.
- Results in a congenital anomaly or birth defect.
- Important medical events that may not result in death, are not life-threatening, or do not require hospitalization may be considered SAEs when, based on appropriate medical judgment, they may jeopardize the patient and may require medical or surgical intervention to prevent one of the outcomes listed in this definition. Examples of such events include allergic bronchospasm requiring intensive treatment in an emergency room or at home, or the development of drug dependency or drug abuse.

### **10.3 Definition of an Adverse Event of Special Interest**

An AESI (serious or nonserious) is one of scientific and medical concern specific to the sponsor's product or program, for which ongoing monitoring and rapid communication by the

investigator to the sponsor can be appropriate. Such an event might warrant further investigation in order to characterize and understand it. Depending on the nature of the event, rapid communication by the trial sponsor to other parties (eg, health authorities or ethics committees) might also be warranted.

Details on the sponsor's currently agreed list of AESIs for rucaparib can be found in the current rucaparib IB. These AESIs are to be reported to the sponsor expeditiously (see [Section 10.8](#) for reporting instructions).

Report any AE of pneumonitis, or any of the following AEs, irrespective of causality assessment and severity, as an AESI within 24 hours using the study Serious Adverse Event Form and the applicable procedures as outlined in Section 10.8:

- pneumonitis
- interstitial lung disease
- pulmonary fibrosis
- acute interstitial pneumonitis
- alveolitis necrotizing
- alveolitis
- hypersensitivity pneumonitis
- organizing pneumonia

#### **10.4 Exceptions to Serious Adverse Event Reporting**

The following are not considered SAEs and therefore are not required to be reported to the sponsor:

- Pre-planned or elective hospitalization, including social and/or convenience situations (eg, respite care).
- Hospital visits of less than 24 hours duration (eg, patient presents to the emergency room, but is not admitted to a ward).
- Overdose of either study drug or concomitant medication, unless associated with an SAE. If the event does not meet SAE criteria, it should still be captured as a non-serious AE on the appropriate eCRF.
- Events of disease progression of the patient's underlying cancer as well as events clearly related to disease progression (i.e., signs and symptoms) should not be reported as a SAE unless the outcome is fatal and occurs during the safety reporting period. If the event has a fatal outcome during the safety reporting period, then the event of Progression of Disease must be recorded as an AE/SAE with CTC Grade 5 (fatal outcome) indicated.
- Diagnosis of progression of disease or hospitalization due to signs and symptoms of disease progression alone should not be reported as a SAE.

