## **10.7 Recording of Adverse Events, Serious Adverse Events, and Adverse Events of Special Interest**

As of the implementation of Amendment 5, only SAEs/AESIs will be fully documented on the appropriate eCRF. For each SAE/AESI, the investigator must provide duration (start and end dates or ongoing), intensity, relationship to study drug, and indicate whether specific action or therapy was required.

Any SAE/AESI that occurs after the first dose of study drug until 28 days after last dose of study drug administration will be collected, documented and reported to the sponsor by the investigator according to the specific definitions and instructions detailed within this protocol, whether dosing has occurred or not. In addition, any AE/SAE that occurs after informed consent is obtained and is deemed related to a screening procedure for the study should also be reported on the AE eCRF and, if applicable, the SAE report form. Events that occur after signing of informed consent but prior to initiation of study drug, unless due to a protocol-mandated procedure, should be recorded on the Medical History eCRF. In order to avoid vague, ambiguous, or colloquial expressions, the AE should be recorded in standard medical terminology rather than the patient's own words. Whenever possible, the investigator should combine signs and symptoms that

constitute a single disease entity or syndrome into a final diagnosis. For example, fever, cough, and shortness of breath may be reported as pneumonia, if that is a reasonable diagnosis.

All SAEs/AESIs that occur during the study or within 28 days after receiving the last dose of study drug, regardless of relationship to study drug, must be reported to the sponsor/designated safety contact immediately (i.e., within 24 hours of the investigator's knowledge of the event). This should be done by faxing or emailing the completed SAE/AESI report to the sponsor/designee contact provided on the SAE/AESI report form. After the 28-day window after treatment discontinuation, only SAEs assessed as related to study drug and all AESIs, irrespective of causality, should be reported. If a patient is determined to be a screen failure, no further AEs/SAEs are required to be reported once that determination has been made, with the exception of AEs/SAEs deemed related to a protocol-specified procedure. Information on the follow-up of AEs, SAEs, and AESIs is provided in [Section 10.7.4](#).

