### **13.6 Case Report Form**

The data will be collected using an electronic data capture (EDC) system by remote data entry on eCRFs. Sites will receive training on the EDC system. All users will be supplied with unique login credentials.

Data collection is the responsibility of the clinical trial staff at the site under the supervision of the site investigator. The investigator is responsible for ensuring the accuracy, completeness, legibility, and timeliness of the data reported.

All source documents should be completed in a neat, legible manner according to the principles of Attributable, Legible, Contemporaneous, Original or Certified Copy, Accurate, and 'Plus' (+) Complete, Consistent, Enduring, and Available (ALCOA+), to ensure accurate interpretation of data. Data recorded in the eCRF should be consistent with the data recorded on the source documents.

Prior to study start, the investigator will prepare a list showing the all individuals delegated responsibility on this study. This "study site personnel and delegation list" must be kept current throughout the study.

Full information regarding electronic data capture and completing eCRFs is included in the investigator files. All questions or comments related to electronic capture should be directed to the assigned monitor.

Data collection will be decreased at the time of implementation of Protocol Amendment 5, as all endpoints except those associated with long-term follow up have been met and reported. As of

the implementation of Protocol Amendment 5, the assessments required to be entered into the study eCRFs/eCRF modules for patients are as follows:

- Log Forms
  - Adverse Events (SAE/AESIs only)
  - Subsequent Anticancer Therapy (SAT)
- TA\_Scan
- EOT
- 28-Day Post
- Long-Term Follow-Up
- Death
- PI\_Sign

Updated eCRF Completion Guidelines will be provided to the sites for further detail regarding what should be entered for patients that are ongoing on treatment or in long-term follow-up at the time Protocol Amendment 5 is implemented.

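### Protocol 10.4 declares hospital visits under 24 hours not to be SAEs without qualification, which conflicts with the SAE definition in 10.2 and, after Amendment 5, also keeps non-AESI events of this kind off the AE eCRF

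*Protocol*

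**What the plan says.** Section 10.2 of the protocol defines an SAE by outcome or consequence. Besides death, the criteria include "Is immediately life-threatening" and "Requires in-patient hospitalization or prolongation of existing hospitalization". None carries a minimum length of stay. The last criterion, important medical events, depends on medical judgment, and its illustration is: "Examples of such events include allergic bronchospasm requiring intensive treatment in an emergency room or at home".

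Section 10.4 opens its list of exceptions with "The following are not considered SAEs and therefore are not required to be reported to the sponsor". The second item is "Hospital visits of less than 24 hours duration (eg, patient presents to the emergency room, but is not admitted to a ward"). The third is qualified: "Overdose of either study drug or concomitant medication, unless associated with an SAE". The progression item that follows is qualified too, since a fatal outcome in the safety reporting period must be recorded as Grade 5.

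On recording, Section 10.7 says: "As of the implementation of Amendment 5, only SAEs/AESIs will be fully documented on the appropriate eCRF". Section 13.6 lists the forms still in use, with the AE log given as "Adverse Events (SAE/AESIs only") and a separate Death form. The synopsis (Safety Assessments) and Table 3, footnote b, agree that AEs are monitored but only SAEs and AESIs are recorded. Section 10.1 still asks the investigator to document every AE and to report AEs on the AE eCRF.

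**The concern.** The lead-in to 10.4 does more than relax a timeline: it states that the listed items are not SAEs. The short-visit item therefore decides the classification of whatever happened during the visit. A site that follows it as written would not report a life-threatening event resolved in the emergency room the same day, or a death there before admission.

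The 24-hour reporting duty in 10.7 and 10.8, and the sponsor's screening for serious and unexpected reactions in 10.8, both depend on the event first being classed as an SAE or AESI. After Amendment 5, entry on the AE eCRF depends on it as well. The synopsis and Section 5.4 add that no further IDMC meetings are planned, so later safety oversight relies on these individual reports.

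**Working it through.** No figure in the plan is involved, so the check compares the sections on concrete cases. Each case is assumed to occur in the safety reporting period and, except in the last row, not to be an AESI.

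| Event in a hospital visit under 24 hours | Section 10.2 | Short-visit item in 10.4, read literally |
|---|---|---|
| Life-threatening event, resolved in the emergency room | SAE | Not an SAE |
| Death in the emergency room before admission | SAE | Not an SAE |
| Bronchospasm treated intensively in the emergency room | SAE if medical judgment so decides | Not an SAE |
| Ward admission shorter than 24 hours | SAE (hospitalization criterion, no time threshold) | Not an SAE if a short admission counts as a hospital visit; the bracketed text is an example, not a limit |
| Event on the AESI list, such as pneumonitis | Depends on the event | Still recorded and reported as an AESI, serious or not (10.3, 10.7, 10.8) |

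1. **Conflict.** In the first two rows the sections give opposite answers without any judgment being involved. These rows carry the point. The third row is supporting only, because 10.2 says that such events may be considered SAEs.

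2. **Missing qualifier.** The overdose and progression items say when the exception lapses; the short-visit item does not. The list also conflicts with itself: fatal progression during a visit under 24 hours must be recorded as Grade 5 under one item and is not an SAE under another.

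3. **Reporting.** Sections 10.7 and 10.8 require SAEs and AESIs to reach the sponsor within 24 hours. They presuppose the classification, so they do not restore an event that 10.4 has removed.

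4. **Recording before Amendment 5.** An event classed as non-serious could still be captured as a non-serious AE. The error would lie in its seriousness and in its reporting.

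5. **Recording after Amendment 5.** By the synopsis, Table 3, 10.7 and 13.6, a non-serious event that is not an AESI has no place on the AE eCRF. Section 10.1 says the opposite. AEs are still monitored and a death goes on the Death form, but that form does not take the place of a 24-hour SAE report.

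6. **Overdose item.** It asks for a non-serious overdose to be captured as a non-serious AE. The AE log in 13.6 no longer takes such entries. This is a separate conflict with the same recording rule.

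**The case against.** The strongest reply is that the item was never meant to override 10.2. It names an encounter, not a medical occurrence; it follows the item on elective hospitalization; and its example, a patient not admitted to a ward, mirrors the in-patient wording of 10.2. On that view it says only that a short visit is not a hospitalization. A list that insists on recording fatal progression is also unlikely to have been meant to exempt a death in the emergency room. This is plausible as intent, but the text does not say it, and no other section supplies the limit. The documents show no site applying the literal rule.

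Three further objections narrow the point, and they stand.

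- A reader might infer that after Amendment 5 these events leave no record anywhere. The documents do not support that: AE monitoring, AESI capture, the Death form and the documentation duty in 10.1 all remain. What is lost is entry of a non-AESI event on the AE eCRF, and 10.1 contradicts even that.
- A reader might infer that the serious-TEAE table in SAP 12.1 is biased downward. That SAP is written to the original protocol and Amendments 1 to 3 (SAP Section 1), with data up to the primary-analysis cut-off (SAP 2.4), so the Amendment 5 recording limit cannot affect it. Whether the short-visit item was in force earlier cannot be told from the current version alone.
- A reader might take the emergency-room bronchospasm example as an automatic SAE. Section 10.2 makes it conditional on judgment.

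**Conclusion.** The conflict between 10.4 and 10.2 is real and should be corrected. Followed as written, 10.4 removes events that are SAEs under 10.2 from 24-hour reporting. This is a rule that gives the wrong answer, not a missing detail.

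Its reach is every event that is serious by a 10.2 criterion and falls within a hospital visit under 24 hours. AESIs are exempt because they are reported regardless. The added loss of AE eCRF entry applies only to patients still on treatment or in follow-up when Amendment 5 was implemented. Section 13.6 describes all endpoints other than long-term follow-up as already met and reported, so that part concerns later safety data. The primary efficacy analysis is not touched.

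The documents give no frequency for such events, so no number can be put on under-reporting, and no bias between arms or in the primary-analysis safety tables is shown. The conclusion assumes that sites apply 10.4 literally; a site that reads it as a gloss on hospitalization would report correctly.

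**What to change.** Limit the short-visit item in 10.4 to the hospitalization criterion. Suggested wording: a hospital visit of less than 24 hours without admission does not by itself meet the hospitalization criterion; the event remains an SAE if it meets any other criterion in Section 10.2.

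Separately, reconcile two passages with the SAE/AESI-only AE log in 10.7 and 13.6: the overdose item's instruction to capture a non-serious overdose as an AE, and the statement in 10.1 that AEs are reported on the AE eCRF. Either the log accepts these entries or the passages are changed to match it.

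The cost is one sentence in 10.4, aligned wording in 10.1 and the overdose item, and a line in the updated eCRF Completion Guidelines that 13.6 already promises. The downside is a few more SAE reports.
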